# 3 Sample size calculation

Sample size is not based on statistical consideration. The planned sample size of approximately 3,000 patients was chosen based on the expected accrual rates and the planned duration of the trial. A large sample size could ensure the precision of the estimate of rare adverse events based on the primary objective of the trial. For example, if incidence rate of an AE is 1%, then the probability of observing at least 30 AEs out of 3,000 patients is 52.47%. For AEs with incidence rate of 2% or higher, the probability of observing at least 30 AEs out 3,000 will be greater than 99.99%.

## 3.1 **Primary analysis**

No formal analysis will be done for hypothesis testing. Safety and efficacy parameters will be summarized in appropriate population.

## 3.2 Power for analysis of key secondary variables

Not applicable.

# 4 Change to protocol specified analyses

No change from protocol specified analysis was made.

# 5 Appendix

## 5.1 Imputation rules

## 5.1.1 Study treatment

The following rule should be used for the imputation of the dose end date for a given study treatment component:

Scenario 1: If the dose end date is completely missing and there is no EOT page and no death date, the subject is considered as on-going:

The subject should be treated as on-going and the cut-off date should be used as the dose end date.

Novartis	Confidential	Page 38
SAP	22-Feb-2022 (1:27)	CLEE011A2404

Scenario 2: If the dose end date is completely or partially missing and the EOT page is available:

Case 1: The dose end date is completely missing, and the EOT completion date is complete, then this latter date should be used.

Case 2: Only Year(yyyy) of the dose end date is available and yyyy < the year of EOT date: Use Dec31yyyy

Case 3: Only Year(yyyy) of the dose end date is available and yyyy = the year of EOT date: Use EOT date

Case 4: Both Year(yyyy) and Month (mm) are available for dose end date, and yyyy = the year of EOT date and mm < the month of EOT date:

#### Use last day of the Month (mm)

All other cases should be considered as a data issue and the statistician should contact the data manager of the study.

After imputation, compare the imputed date with start date of treatment, if the imputed date is <start date of treatment:

#### Use the treatment start date

Subjects with missing start dates are to be considered missing for all study treatment component related calculations and no imputation will be made. If start date is missing then end-date should not be imputed.

#### 5.1.2 AE, ConMeds and safety assessment date imputation

 Table 5-1
 Imputation of start dates (AE, CM) and assessments (LB, EG, VS)

Missing Element	Rule
day, month, and year	• No imputation will be done for completely missing dates
day, month	
 
If available year = year of study treatment start date then         
 
If stop date contains a full date and stop date is earlier than study treatment start date then set start date = 01JanYYYY
 
Else set start date = study treatment start date.
 
 
 
If available year > year of study treatment start date then 01JanYYYY
 
If available year < year of study treatment start date then 01JulYYYY
 

Novartis SAP

Missing	Rule
Element	
day	• If available month and year = month and year of study treatment start
	date then
	
 
If stop date contains a full date and stop date is earlier than study treatment start date then set start date= 01MONYYYY.
 

	$\circ$ Else set start date = study treatment start date.
	• If available month and year > month and year of study treatment start date then 01MONYYYY
	• If available month and year < month year of study treatment start date then 15MONYYYY

Table 5-2	Imputation of end dates (AE, CM)
Missing	Rule
Element	(*=last treatment date plus 30 days not > (death date, cut-off date, withdrawl
	of consent date))
day, month, and year	• Completely missing end dates (incl. ongoing events) will be imputed by the end date of the on-treatment period*
day, month	• If partial end date contains year only, set end date = earliest of 31DecYYYY or end date of the on-treatment period *
day	• If partial end date contains month and year, set end date = earliest of last day of the month or end date of the on-treatment period*

Any AEs and ConMeds with partial/missing dates will be displayed as such in the data listings.

Any AEs and ConMeds which are continuing as per data cut-off will be shown as 'ongoing' rather than the end date provided.

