#### Baseline

For safety and efficacy evaluations, the last available assessment on or before the date of start of study treatment is defined as "baseline" assessment.

In rare cases where multiple measurements meet the baseline definition, with no further flag or label that can identify the chronological order, then the following rule should be applied: If multiple values are from the same laboratory (local) or collected for Electrocardiograms (ECGs) or vital signs, then the last value should be considered as baseline.

If patients have no value as defined above, the baseline result will be missing.

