## Multiple lab assessments

Specific rules for defining the baseline when there are multiple lab measurements taken at the last assessment date on or before the start date of study treatment are presented below:

As a general rule the lab value among the multiple measurements with the lowest CTCAE grade will be considered as the baseline value.

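### SAP Table 5-1 can date a partly dated on-treatment lab or ECG to Day 1, where it may become baseline; separately, the SAP gives two conflicting tie rules for lab baselines

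*SAP*

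**What the plan says.** SAP 5.1.2, Table 5-1, sets one imputation rule for "Imputation of start dates (AE, CM) and assessments (LB, EG, VS". It has two triggers that lead to the treatment start date:

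- Day missing: "If available month and year = month and year of study treatment start" date.
- Day and month missing: "If available year = year of study treatment start date then".

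Under either trigger there is one exception: "If stop date contains a full date and stop date is earlier than study treatment start date then set start date" to the first of that month or year. Otherwise the instruction is "Else set start date = study treatment start date". Records whose known part does not match treatment start go elsewhere (first of the month or 1 January if later, the 15th or 1 July if earlier), and completely missing dates are not imputed.

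SAP 2.1.3 says that "the last available assessment on or before the date of start of study treatment is defined as" baseline. If several values qualify and nothing shows their order, then for values from the same local laboratory, and for ECGs and vital signs, "then the last value should be considered as baseline". SAP 5.3 has a different rule for several lab values on the last date on or before treatment start: "As a general rule the lab value among the multiple measurements with the lowest CTCAE grade will be considered as the baseline value".

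Nothing in the SAP keeps an imputed date out of baseline selection or lets the visit label override it.

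**The concern.** For adverse events, moving an unclear start to Day 1 is the cautious choice, because the event then counts as treatment-emergent. For a measurement it can do the reverse: an on-treatment value becomes the reference against which later values are judged, and stops counting as a post-baseline value.

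Labs and ECGs are the exposed data. In protocol Table 7-1 haematology, chemistry and ECG are collected at screening and next at C1D15, with nothing scheduled on C1D1. The true baseline will therefore usually carry a date before Day 1, and a record imputed to Day 1 beats it outright. C1D15 and C2D1 are the only scheduled on-treatment ECGs before end of treatment, and protocol 4.3 reports that QTc prolongation in the earlier phase III trial was seen in the first two cycles. A misplaced C1D15 ECG removes one of those two readings and can hide a QTcF increase from baseline. A misplaced C1D15 lab can hide a grade shift or remove a worst post-baseline grade.

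The lab tie rules are a second, smaller matter. All scheduled labs are local (protocol 7.2.2.5), so both rules can apply to the same pair of values and give different baselines. Choosing the lowest grade as baseline inflates shifts.

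**Working it through.** The plan attaches no figure to this rule, so there is none to reproduce. The check applies the rules in sequence and then counts dates.

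**Worked example.** Treatment starts 3 May 2017. The screening value is dated 28 April 2017. The C1D15 value is truly from 17 May but is recorded as May 2017.

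1. The known month and year match treatment start, so the first trigger applies.
2. A lab, ECG or vital-sign reading has no stop date, so the exception cannot apply. Table 5-2 imputes end dates for AE and CM only.
3. The C1D15 record is dated 3 May 2017.
4. The last assessment on or before 3 May is now the C1D15 value. The 28 April value is displaced.

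**How often a partial date would do this.** Assumptions: treatment starts are spread evenly over calendar days, and visits fall on their nominal day. C1D15 is start + 14 days; C2D1 is start + 28 days.

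With only the day missing, C1D15 stays in the start month on 17 start days of a 31-day month, 16 of a 30-day month and 14 of a 28-day February:

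- 2017: 7 × 17 + 4 × 16 + 14 = 197; 197/365 = 54.0%.
- 30 November 2016 to 22 March 2018 (first to last patient first visit, 478 days): 0 + 17 + 197 + 17 + 14 + 17 = 262; 262/478 = 54.8%.

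For C2D1 the counts are 3, 2 and 0 days per month type:

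- 2017: 7 × 3 + 4 × 2 + 0 = 29; 29/365 = 7.9%.
- Enrolment period: 0 + 3 + 29 + 3 + 0 + 3 = 38; 38/478 = 7.9%.

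From C2D15 (start + 42 days) the share is zero. With day and month both missing, only the year must match; for 2017, C1D15 gives (365 − 14)/365 = 96.2%.

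| Record | Day missing | Day and month missing |
|---|---|---|
| C1D15 | 54-55% | 94-96% |
| C2D1 | about 8% | 88-92% |
| C6D1 | 0% | 62-64% |

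These shares are conditional on the date being partial.

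**Illustrative size.** The documents give no rate of partial dates. If 0.1% to 1% of C1D15 dates lacked the day (an assumption), then with 3,246 treated patients (protocol Amendment 04 rationale):

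- 3,246 × 0.001 × 0.548 = 1.8
- 3,246 × 0.01 × 0.548 = 17.8

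That is about 2 to 18 patients per parameter with a displaced baseline. It is not a count of lost events. At the 3.3% rate of QTcF above 480 ms in the earlier trial (protocol 1.2.1.2.1), those patients would include 1.8 × 0.033 = 0.06 to 17.8 × 0.033 = 0.6 with such a value.

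**Vital signs.** Table 7-1 schedules these at C1D1 and next at C2D1, so the C1D15 share does not apply. The relevant day-missing share is about 8%, and a dated C1D1 reading would create a tie, not a displacement.

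**Do the tie rules repair it?** No. They operate only when another value is also dated Day 1. For labs, the lowest-grade rule would then keep a worse on-treatment value out of baseline but let a better one in.

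**The case against.** The strongest reply is that this will hardly ever occur. Protocol 9.3 and 9.4 provide automatic checks at data entry, queries for missing values and verification before lock, so few lab or ECG dates should remain partial. The study tests no hypothesis, and the affected displays are descriptive. That stands, and it is why the effect is likely to be small.

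Several stronger readings are tempting but not supported:

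- A reader might infer that the neutropenia, febrile neutropenia or QT prolongation counts are biased. They are not. The primary and AESI counts come from reported adverse events (SAP 2.5 and 2.8.2), and clinically significant lab and ECG findings must be recorded as adverse events (protocol 7.2.2.5 and 7.2.2.6.1).
- A reader might infer that every partial date moves to Day 1. Only those whose known part matches treatment start do so.
- A reader might infer that the rule always misleads. For a genuine screening or pre-dose C1D1 record, dating it to Day 1 keeps it eligible for baseline, as it should be.
- A reader might infer that the worst grade is always lost. That needs C1D15 to be the only worst value. Labs are repeated at C2D1, C2D15, C3D1, C4D1, C5D1 and C6D1, and protocol Table 6-5 calls for repeat ECGs after a QTcF of 481 ms or more.

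On the tie rules, SAP 2.1.3 is confined to rare cases where order cannot be established and, for labs, to values from the same laboratory. The overlap with SAP 5.3 is therefore narrow, but within it the two instructions conflict.

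What the reply does not remove is that a written rule, followed as written, gives a wrong baseline.

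**Conclusion.** The point holds within limits. Table 5-1 and the baseline definition together allow a C1D15 lab or ECG with a missing day to replace the dated screening value and drop out of the post-baseline data. Given such a partial date, this happens for about 54-55% of start dates, assuming evenly spread starts and nominal visit days; for C2D1 records it is about 8%. The exposed outputs are the lab shift and worst-grade tables, the QTcF notable-value and change-from-baseline summaries and, to a lesser extent, notable vital signs. The primary AE and AESI counts are not affected.

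The overall size cannot be fixed from the documents because the rate of partial dates is not given. With the data checks described it is probably low, so a few patients at most are likely to be affected; the upper figure of 18 needs an assumed rate of 1%. The case for correcting it rests on the rule being wrong and cheap to repair, in a trial whose primary objective is safety. The lab tie-rule conflict is real, of unknown and probably small effect.

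**What to change.** 1. In SAP Table 5-1, limit imputation to the treatment start date to AE and CM records.
2. Place partly dated lab, ECG and vital-sign records by visit label: screening or pre-dose C1D1 records are eligible for baseline; C1D15 or later records are on-treatment.
3. State that a record with a post-dose label, or with an imputed date and no label showing it is pre-dose, cannot be baseline. A ban on all imputed dates would go too far, since it would discard screening-labelled values that are clearly pre-dose.
4. Keep the last-value tie rule in SAP 2.1.3 and delete the lowest-grade sentence in SAP 5.3.

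With steps 1 to 3, the share of partly dated post-dose records entering baseline falls to zero; in the example, the 28 April value stays as baseline.

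The cost is SAP wording and a small program change, with no new data. If the Core Phase database is already locked, count the partly dated records first, rerun the exposed tables and footnote any change.

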## 5.1.2.1 Other imputations

# Incomplete date of initial diagnosis of cancer and date of most recent recurrence

Missing day is defaulted to the 15th of the month and missing month and day is defaulted to 01-Jan.

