#### Time unit

A year length is defined as 365.25 days. A month length is 30.4375 days (365.25/12). If duration is reported in months, duration in days will be divided by 30.4375. If duration is reported in years, duration in days will be divided by 365.25.

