## 2.3.2 Diagnosis and extent of cancer

Summary statistics will be tabulated for diagnosis and extent of cancer. This analysis will include the following: primary site of cancer, histological grade, stage at initial diagnosis,

Novartis	Confidential	Page 20
SAP	22-Feb-2022 (1:27)	CLEE011A2404

stage at time of study entry, time since initial diagnosis, time from initial diagnosis to first recurrence/progression (in months), presence/absence of target and non-target lesions, HER2/Estrogen/Progesterone receptor status, number and type of metastatic sites involved.

The numbers and percentages of patients in the category defined by presence/absence of target and non-target lesions will be based on the data collected on RECIST target/non-target lesion assessment eCRF pages. Metastatic sites will be based on diagnosis page.

Time since initial diagnosis and Disease-free-interval will be summarized in months. This data will also be categorized into time intervals. Frequency counts and percentages will be presented for the number of patients in each interval.

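### A diagnosis date known only by year is set to 01 January, so time since initial diagnosis is overstated by about 6 months on average in those records; only descriptive baseline summaries are affected

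*SAP*

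**What the plan says.** The rule stands in SAP 5.1.2.1 under the heading "Incomplete date of initial diagnosis of cancer and date of most recent recurrence". It has two parts. For a day alone, "Missing day is defaulted to the 15" (of the month). For month and day together, "missing month and day is defaulted to 01-Jan".

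The dates feed SAP 2.3.2: "Time since initial diagnosis and Disease-free-interval will be summarized in months. This data will also be categorized into time intervals". The cut points of those intervals are not given. The same section lists the interval from diagnosis to first recurrence or progression.

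Table 5-1 (SAP 5.1.2) covers AE and medication start dates and safety assessment dates. When month and day are missing and the recorded year is earlier than the "year of study treatment start date then 01JulYYYY" applies, a mid-year default. The SAP has no rule that caps, checks or corrects the diagnosis and recurrence dates after imputation.

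**The concern.** The two defaults sit side by side, for the same two variables, and behave differently. The 15th is close to the middle of the dates it stands for, so errors roughly cancel. 01 January is the lower end of the dates it stands for, so errors cannot cancel: the imputed diagnosis is never later than the true one. No reason is given for the difference.

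At stake is the accuracy of a baseline description, reported in months and in categories, of a population that the protocol presents as broader than that of the other Phase III ribociclib studies. A one-directional error moves the summary statistics of time since diagnosis upward and can move patients into a longer category.

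The rule also lacks an ordering check. A year-only recurrence in the same year as a fully dated diagnosis is placed on or before that diagnosis.

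**Working it through.** The plan states no figure on this point, so there is none to reproduce.

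**Inputs.** From the SAP: 01 January for missing month and day and the 15th for missing day (5.1.2.1); 01 July for earlier years (Table 5-1); a month of 30.4375 days (2.1.3). From the protocol's amendment rationales, used only to illustrate the same-year case: first patient first visit on 30-Nov-2016 and last on 22-Mar-2018. Assumption, not in the documents: the true date is uniform over the days of the year.

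**Error per record.** Error = true date minus imputed date; a positive error lengthens time since diagnosis by the same amount. In a 365-day year the offsets from 01 January run from 0 to 364.

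| Default | Mean error | Range | Mean absolute error |
|---|---|---|---|
| Month and day to 01 January | (0 + 364)/2 = 182 days; 182/30.4375 = 5.98 months | 0 to 364/30.4375 = 11.96 months | 5.98 months |
| Month and day to 01 July (offset 181) | 182 − 181 = 1 day; 0.03 months | −5.95 to 6.01 months | 3.00 months |
| Day only to the 15th | 0.7 days; 0.02 months | −14 to +16 days | not needed |

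In a leap year the 01 January mean is 182.5 days, or 6.00 months.

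**Diagnosis in the year treatment starts.** The true date cannot be later than treatment start, so the overstatement is smaller. For a start on 22-Mar-2018 the offsets run from 0 to 80: mean 40 days, 40/30.4375 = 1.3 months. For a start on 30-Nov-2016 they run from 0 to 334: mean 167 days, 167/30.4375 = 5.5 months.

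**Cohort mean.** If a share f of records lacks the month, the mean shifts by f × 5.98 months.

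| f | Shift in mean time since diagnosis |
|---|---|
| 1% | 0.06 months |
| 5% | 0.30 months |
| 10% | 0.60 months |
| 30% | 1.79 months |

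**Disease-free interval, if it is recurrence minus diagnosis.** Let a and b be the true offsets of diagnosis and recurrence within their years, taken as independent and in different calendar years.

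- Only the diagnosis month is missing: shift +a, mean +5.98 months.
- Only the recurrence month is missing: shift −b, mean −5.98 months.
- Both are missing: shift a − b, mean 0, SD 4.9 months, range −11.96 to +11.96 months.

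**Ordering.** This needs no distribution. Take a diagnosis fully dated 01 September and a recurrence known only by the same (non-leap) year. Recurrence is set to 01 January, 243 days before diagnosis, and the interval is −243/30.4375 = −8.0 months.

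**The case against.** The strongest case against is that this is a convention for a few descriptive rows. Much of it stands.

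- **No denominator.** A reader might infer that the trial's time since diagnosis is overstated by 6 months. The documents do not support that. The figure applies only to records without a month, and their share is not given.
- **Disease-free interval is not defined.** A reader might infer that it is biased under this rule. The SAP does not say which dates enter it. The imputation rule names the most recent recurrence, whereas SAP 2.3.2 lists the first recurrence or progression. The protocol's own use of the term, in exclusion criterion 3, counts from the end of (neo)adjuvant treatment to study entry and needs neither date. The shifts shown for this interval are therefore conditional, and they average zero when both dates are year-only.
- **Importance.** A reader might see these variables as markers of endocrine sensitivity, or as the basis of a comparison with the pivotal trials. The documents give them neither role: the study is declared non-comparative, tests no hypothesis, and includes neither variable among its subgroups.
- **Table 5-1 is not a single convention.** It also uses 01 January in some cases, such as a year after treatment start, and serves to place events relative to treatment. So 5.1.2.1 differs from it without contradicting it. Still, its case closest to a historical diagnosis, a year before treatment start, is the one that takes 01 July.
- **01 July has its own problem.** It can fall after consent or treatment start, or place recurrence before diagnosis, so it needs a feasibility rule.

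None of this removes the core point: for a year-only diagnosis the stated default can err in one direction only, and nothing later in the SAP corrects it.

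**Conclusion.** The point holds as a low-severity improvement. In records where the diagnosis is known only by year, time since initial diagnosis is overstated by about 6 months on average (0 to 12), assuming true dates are spread evenly over the year, and by less when diagnosis falls in the treatment-start year. The direction does not depend on that assumption; the size does.

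The effect on the whole cohort cannot be stated, because the share of such records is unknown; at 10% it would be 0.6 months in the mean. The number of patients who would change category cannot be stated either, because no cut points are given. The effect on disease-free interval depends on a definition that the SAP does not supply.

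It would be wrong to extend the point to the trial's conclusions. AE endpoints, TTP, ORR, CBR and the subgroups in SAP 2.2.6 do not use these dates.

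**What to change.** In SAP 5.1.2.1, default a missing month and day to 01 July, in line with Table 5-1 for earlier years. Where 01 July is infeasible, because it falls after consent or treatment start or would put recurrence before diagnosis, use the midpoint of the feasible range. For a diagnosis in 2018 with treatment start on 22-Mar-2018, bounding by treatment start alone for simplicity, that is 10 February (offset 40 of 0 to 80). In the September example above, 01 July would still precede the diagnosis, so the midpoint of 01 September to 31 December applies. Report the number of imputed diagnosis and recurrence dates beside the summaries. It would also help to state in SAP 2.3.2 which dates define disease-free interval.

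For time since diagnosis in earlier years this takes the mean error from 182 days to about 1 day and halves the mean absolute error, from 5.98 to 3.00 months. The cost is a short SAP edit and a few extra lines of derivation code for the feasibility rule.
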